week Double-Blind Placebo Controlled Withdrawal phase. Patients who do not exhibit the required weight loss of at least 5 kg will be withdrawn from the treatment, but should continue with the study assessments.

During this time, patients will be assigned to the 4-week sequence in which they receive placebo in a double-blinded sequence. The key objective of this phase is to implement the only double-blind, placebo-controlled period for this study that will inform patient's symptomatic hunger and weight change responses to stopping and then restarting active therapy with setmelanotide without awareness of the timing of the withdrawal.

Next, patients will resume with Open Label Active Treatment for an additional ~32 weeks, for a total of ~52 weeks of treatment at the individual patient's therapeutic dose (inclusive of the 4-week placebo withdrawal).

Study Procedures

The primary efficacy endpoint is the proportion of patients in the full analysis set (FAS) who meet the $\geq 10\%$ weight loss threshold (responders) after ~1 year of treatment, compared to the proportion from historical data (at most 5% responders in the null population). Therefore, frequent weight measurements will be obtained throughout the course of the trial. Supporting efficacy endpoints will include: Hunger assessed daily by a questionnaire (using a numeric rating scale for patients 12 years or older and [REDACTED]

[REDACTED] as well as by 2 Global Hunger Questions for each patient over time, including during the Screening Period; body composition assessments including total body weight loss, fat loss, and [REDACTED], measured in kg as well as percent change from baseline; and waist circumference.

The safety and tolerability of setmelanotide QD SC injection will be assessed by the frequency and severity of adverse events (AEs) as well as changes in physical examinations, electrocardiograms (ECGs), vital signs (including resting BP and HR), laboratory evaluations, and injection site reactions.

Potential improvements in [REDACTED] [REDACTED] as well as glucose parameters as measured by fasting glucose, HbA1c and OGTT with focus on parameters of insulin sensitivity will be assessed over time.

[REDACTED]

[REDACTED] . As required by Food and

	
Drug Administration (FDA) for central nervous system (CNS)-active obesity medications, changes in [REDACTED] [REDACTED] will be monitored over the entire course of the trial.

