After establishing a patient's individual therapeutic dose, the patient will continue dosing for an additional 10 weeks, resulting in 12 total weeks of treatment at their therapeutic dose (including the last 2 weeks at the therapeutic dose in the dose titration phase). To continue treatment after 12 weeks of treatment at their therapeutic dose, patients must achieve a weight loss of 5 kg or greater from baseline if their baseline weight was greater than 100 kg or a weight loss of > 5% from baseline if their baseline weight was < 100 kg. Patients who do not achieve these weight loss criteria will be discontinued from treatment, but should continue with other study procedures through study end.

[figure not shown]
Placebo-Controlled, Double-Blinded Withdrawal Phase (8 weeks)

Patients that achieve a 5 kg or 5% weight loss after 12 weeks of treatment at their therapeutic dose will receive either placebo or active for four weeks and then cross-over to the opposite treatment for four weeks. The treatment assignment during the first four-week period will be double-blinded so that the sites and patients do not know if their first four-week block of treatment is placebo or active.

Open Label Treatment Phase (32 weeks)

After completing the placebo-controlled, double-blinded withdrawal phase, patients will continue dosing at their individual therapeutic dose for an additional 32 weeks. At the end of the 32 weeks, patients can enroll in a separate long-term extension study to continue receiving setmelanotide (Study RM-493-022) or they can complete treatment with a final visit approximately 30 days after their last dose.

Figure 7: Study Schema

It is anticipated that at least 10 patients will be enrolled in this study. However, due to the ultra-rare prevalence of this population, if more patients are identified during the conduct of the study, they may also be enrolled.

In addition, for patients at sites where feasible, and who agree to participate, [REDACTED]

[REDACTED]

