4.5. Withdrawal of Patients

Patients will be informed that they have the right to withdraw from the study at any time for any reason, without prejudice to their medical care. The Investigator also has the right to withdraw patients from the study, after discussion with the sponsor, for any of the following reasons:

- AEs, which justify ceasing treatment. Specific predefined events for discontinuation, as well as additional guidelines for safety monitoring, are included in Appendices 11.4 – 11.7.
- Non-adherence to study drug regimen or protocol requirements.
- Non-compliance with instructions or failure to return for follow-up.
- Failure to demonstrate 5 kg of weight loss (or 5% if baseline body weight is <100 kg) at the end of the 10-week open label treatment phase.

If a patient is withdrawn from treatment or discontinued from the study, the primary reason is to be recorded in the source documents/case report form (CRF).

All patients who are no longer receiving active treatment prior to completing the ~ 1 year treatment period should be strongly encouraged to complete all remaining visits and procedures as outlined in the Schedule of Assessments in Section 6.

In case of withdrawal from the study (i.e. withdrawing consent), all adverse events should be followed as described in Section 7.4; any skin adverse experiences should continue to be followed, if at all feasible, for ~60-90 days to confirm near, or complete resolution (as has been shown in previous studies).

Rhythm will provide support for patient and caregiver travel, will make available visiting home health care professionals, and any other necessary logistical support to ease the burden on the patient to facilitate compliance.

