Following the 10-week open label active treatment phase, patients will begin the 8-week double-blind placebo-controlled withdrawal period where patients will be assigned to the 4-week sequence in which they receive placebo in a double-blinded sequence. The key objective of this phase is to implement the only double-blind, placebo-controlled period for this study that will inform patient’s symptomatic hunger and weight change responses to stopping and then restarting active therapy with setmelanotide without awareness of the timing of the withdrawal. Given this short, maximum 4-week interval, it is expected that all subjects will be able to tolerate and report on symptoms and weight changes during this double-blind, placebo-controlled phase. If patients are not able to tolerate the anticipated weight gain and return of symptoms of hunger, patients may be allowed to resume open label active treatment upon discussion and agreement from Rhythm. Any such agreement will be documented in writing and approved by Rhythm prior to resuming the patient on active treatment.

Thereafter patients will resume open label active treatment for an additional ~32 weeks, for a total of ~52 weeks of treatment at the individual patient’s therapeutic dose (inclusive of the 4-week placebo withdrawal).

Following the dose titration and 10-week open label active treatment phases, only patients who lose at least 5 kg of weight from baseline (or 5% if baseline weight < 100 kg), and who continue to show tolerability to setmelanotide, will continue into the rest of the study. Patients who do not exhibit the required weight loss will be withdrawn from the study, and complete the Early Termination Visit.

For patients who complete the study but do not wish to enroll into the future long-term extension study (as noted in Section 5.5), patients will be required to return for a Final Visit ~30 days after the last dose of setmelanotide, for a final follow-up safety assessment. Any ongoing AEs reported at this visit should be monitored as outlined in Section 7.4. For patients who enroll in the future long-term extension protocol, this visit is not required.

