Any patient withdrawing from the study will complete the Early Termination Visit, if possible, and will be encouraged to complete all remaining study visits. For those patients not willing to complete study visits at the clinic, home health care practitioner visits or telephone follow-up may be acceptable to obtain minimum patient self-reported data (i.e.: weight, AEs, etc.).

Detailed descriptions of the safety, PD and █ procedures to be conducted during this study are provided in the sections below. The amount of blood volume to be drawn for these procedures is within the acceptable limits for each visit and over the duration of the study (Appendix 11.12). However, blood draws may be challenging in this population of extremely obese patients due to poor access to their veins. In these instances, the PI should contact the Medical Monitor to prioritize sampling, with samples being collected for safety the highest priority.

Patients will be required to fast overnight on the day preceding all visits, beginning with the initial Screening Visit. Patients will be allowed to take their usual medications with a sip of water on the morning of each clinic visit.

The Screening Period can occur within ~ 4 weeks of Day 1 and should be scheduled within this timeframe to allow test results to be received and continued eligibility of patients confirmed prior to the first dose on Day 1. Assessments may occur over multiple days during the Screening Period. All screening bloodwork should be collected between Study Day -28 and -14 in order to ensure the WHO maximum cumulative blood volumes are not exceeded over the course of the study. To obtain sufficient baseline data on symptoms of hunger (collected daily), the screening period should be a minimum of two weeks and up to four weeks.

To provide flexibility to the patient and study staff for the number of clinic visits, the actual scheduling of clinic visits can allow flexibility in timing of visits. During the Dose Titration phase, the goal will be for visits to occur within +/- 3 days. But as this patient population is ultra-rare, all data collected, even if outside of visit windows, will be included in all analyses of endpoints.

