7 Once the patient's individual therapeutic dose is established the patient will enter the Open Label Active Treatment phase for 10 additional weeks, for a combined total of 12 weeks of dosing at the therapeutic dose. During this time, the study calendar will be reset, starting when the therapeutic dose was initiated (i.e. the last 2 weeks of dose titration when the therapeutic dose was established). Therefore, the Open Label Active Treatment phase starts at the beginning of Week 3 (V3). Patients losing 5 kg of weight (or 5% if baseline weight $<$ 100 kg) at the end of the Open Label Treatment phase will enter the Double-Blind Placebo Controlled Withdrawal phase lasting 8 weeks.

8 Upon completion of the Double-Blind Placebo Controlled Withdrawal phase, patients will resume Open Label Active Treatment for an additional ~32 weeks.

9 Early Termination: For those patients who withdraw consent or are withdrawn and not willing to complete the remaining study visits, the early termination visit assessments should be performed, when possible. Additionally, patients who withdraw and are not willing to return for the remaining clinic visits can be contacted via phone, if amenable, to collect self-reported patient data (i.e.: weight, hunger, AEs, etc.). Final Visit: For patients who complete the study but do not wish to enroll into the future long-term extension study (as noted in Section 5.5), patients will be required to return for a Final Visit ~30 days after the last dose of setmelanotide, for a final follow-up safety assessment. Any ongoing AEs reported at

this visit should be monitored as outlined in Section 7.4. For patients who enroll into the long-term extension study, this visit is not required.

10

[REDACTED]

11 Weight is to be measured at the clinic using the same scale after patients have emptied their bladder and while fasting. Patients are to wear light clothing or underwear, no shoes, and will be weighed at approximately the same time of day. Weight measurements are to be done in triplicate; waist circumference will be single measures.

12 Extra retain samples will consist of 2 serum and 2 plasma (K2EDTA) vacutainer tubes.

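### Section 6.1 withdraws patients who fail the 12-week weight-loss gate from the study, while the synopsis and Section 3.1 keep them in follow-up off treatment

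*Protocol*

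**What the plan says.** The gate falls after 12 weeks at the therapeutic dose and requires a loss of 5 kg, or 5% for patients under 100 kg at baseline. On what follows a failed gate, the protocol says:

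- **Synopsis of Study Activities:** these patients "will be withdrawn from the treatment, but should continue with the study assessments".
- **Section 3.1, Open Label Phase:** they "will be discontinued from treatment, but should continue with other study procedures through study end".
- **Section 4.5:** "The Investigator also has the right to withdraw patients from the study, after discussion with the sponsor, for any of the following reasons". Gate failure is on the list that follows. The section then says that patients off active treatment before about 1 year "should be strongly encouraged to complete all remaining visits and procedures".
- **Section 6.1, paragraph on the gate:** only patients who pass go on to the remainder of the study. For the others: "Patients who do not exhibit the required weight loss will be withdrawn from the study, and complete the Early Termination Visit".
- **Section 6.1, two paragraphs later:** "Any patient withdrawing from the study will complete the Early Termination Visit, if possible, and will be encouraged to complete all remaining study visits". Home-health visits or telephone contact are acceptable for patients unwilling to come to the clinic.
- **Table 6-1, footnote 9:** the early termination assessments apply "For those patients who withdraw consent or are withdrawn and not willing to complete the remaining study visits".

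Section 8.2 includes all available measurements in the FAS analysis, and names data from patients who stop active treatment. Section 8.1 counts a patient with no data after month 10 as not having lost 10%.

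**The concern.** A patient cannot be withdrawn from the study and also continue its procedures to the end. Section 4.5 treats withdrawal from treatment and discontinuation from the study as different states. The gate paragraph of 6.1 merges them, and 6.1 is where a site looks to see which visits to hold.

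The patients concerned are by definition those who have lost least at week 12, so any loss of their data is selective. The outcomes exposed are the 1-year changes in weight, fat mass, waist circumference, hunger and glucose parameters. The primary objective in 2.1.1 is itself worded as percent weight change. The SAP can set rules for missing values, but it cannot recover assessments that were never made.

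**Working it through.** **1. The rules side by side**

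| Place | Treatment | Study follow-up after a failed gate |
|---|---|---|
| Synopsis | stopped | assessments continue |
| 3.1 | stopped | procedures continue to study end |
| 4.5 | not stated separately | withdrawal at the investigator's discretion; patients off treatment strongly encouraged to attend |
| 6.1, gate paragraph | not stated separately | withdrawn; Early Termination Visit |
| 6.1, later paragraph | not stated separately | Early Termination Visit if possible; encouraged to attend |
| Footnote 9 | not stated separately | early termination assessments for those who withdraw consent, or are withdrawn and unwilling to attend |

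The direct conflict is between the gate paragraph of 6.1 and the synopsis and 3.1. Section 4.5 adds a discretionary version.

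**2. The plan's own figures**

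The test is an exact binomial with N = 10, null 5%, and success at 3 or more responders.

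- Type I error: P(X ≥ 3 | 0.05) = 0.0115. With 2 or more it would be 0.0861, so 3 is the right threshold.
- Power at true proportions 0.4 and 0.5: 0.833 and 0.945, as in the Section 8.1 table. The other tabulated values from 0.2 to 0.7 also reproduce.

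**3. Effect on the primary endpoint**

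Titration lasts 2 to 12 weeks and the open-label phase 10 weeks, so the gate falls 12 to 22 weeks after the first dose, well before month 10. A patient withdrawn there has no later weight, counts as a non-responder under 8.1, and stays in the FAS denominator. The 3-of-10 threshold and the 0.0115 are unchanged.

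The choice of rule alters the count only if a gate failure would reach 10% loss by 1 year, and then withdrawal is the conservative reading. An illustration, assuming 20% gate failures and 50% response among those who pass:

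- Withdrawn: p = 0.8 × 0.5 = 0.40, power 0.833.
- Followed, with 10% of failures responding: p = 0.40 + 0.2 × 0.1 = 0.42, power 0.863.
- Followed, with 20% responding: p = 0.44, power 0.889.

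**4. Effect on a 1-year mean (assumed values, none from the protocol)**

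Let k be the number of gate failures among 10, f their 1-year percent weight change (0 to −4), and c that of continuers (−10 to −20). If lost patients drop out of the mean, it becomes too favourable by (k/10)(f − c):

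- k = 1: 0.1 × (−4 + 10) = 0.6, to 0.1 × (0 + 20) = 2.0 points
- k = 2: 1.2 to 4.0 points
- k = 3: 1.8 to 6.0 points

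Example: with k = 2, f = −2 and c = −15, the mean of all 10 is (8 × −15 + 2 × −2)/10 = −12.4. The continuers' mean is −15.0, a shift of 2.6.

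If the early termination weight is carried forward instead, the loss at the gate is at most about 5%: the 5% limit applies under 100 kg, and less than 5 kg is under 5% from 100 kg upward. If weight is back at baseline by 1 year, the shift is at most (k/10) × 5 = 0.5, 1.0 or 1.5 points for k = 1, 2 or 3.

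Neither set of figures is an upper bound. Weight above baseline at 1 year would enlarge both.

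**5. How likely is a failure?**

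The chance of at least one gate failure in 10 is 1 − (1 − r)^10. For assumed rates r of 10%, 20% and 30% it is 0.65, 0.89 and 0.97.

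**The case against.** The strongest reply is that the protocol already seeks continued attendance. Section 4.5 and the later paragraph of 6.1 both encourage it, and footnote 9 presupposes that some withdrawn patients keep coming. No protocol can compel attendance, so what remains is one loosely worded sentence. Much of this stands: data are lost only where a site stops at the gate paragraph or the patient declines. But encouragement after an ordered withdrawal is weaker than the instruction in 3.1 to continue. The telephone fallback yields self-reported weight, not the fasting, triplicate clinic weight of footnote 11.

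Three stronger readings are tempting and are not supported.

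- *The primary result is biased or underpowered.* It is not. The missing-data rule and the FAS denominator protect it.
- *Section 8.2 depends on these data and fails without them.* It includes whatever measurements are available, and it stays true under either follow-up rule.
- *The secondary results are biased by a known amount.* The protocol leaves missing-data handling to the SAP, which is not at hand, and the shifts above rest wholly on assumed values.

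**Conclusion.** The contradiction is real and stands in the current text. Its consequence is limited to possible selective loss of 1-year continuous and secondary data from the poorest early responders, data for which 8.2 makes provision. The size is unknown: zero if nobody fails the gate or all failures attend, and about 0.6 to 2.0 points of mean percent weight change per lost patient under the observed-case assumptions above. No stated power or alpha figure is wrong. With about 10 patients, one or two such losses can visibly change a mean. The point is worth correcting, but it does not threaten the primary conclusion.

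**What to change.** Reconcile the gate paragraph of 6.1 with the synopsis, 3.1, 4.5, the later paragraph of 6.1 and footnote 9 to Table 6-1, so that one follow-up rule applies. It should separate being off treatment from being withdrawn from the study, and keep gate failures, with their agreement, in the scheduled assessments through the 1-year visit. Section 8.2 needs no change.

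On the Early Termination Visit, only make 6.1, 7.5 and footnote 9 agree. Do not narrow who receives it: 6.1 gives it to any patient who withdraws, 7.5 encourages it after withdrawal from treatment for an adverse event, and it carries safety assessments, including a skin examination. This point takes no position on the gate or on stopping treatment.

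The cost is wording. The visits are already in the schedule, and 6.1 already allows home-health visits. The downside is about 52 − 12 = 40 weeks of visits without study drug for gate failures, and 1-year secondary means that may look less favourable.

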5. STUDY TREATMENTS

5.1. Study Drugs

All study drugs are for investigational use only and are to be used only within the context of this protocol. All investigational study drugs (setmelanotide and placebo) will be supplied by Rhythm.

Setmelanotide drug product (RM-493-mPEG/DSPE formulation) is a sterile solution for injection. The product is manufactured at a concentration of 10.0 mg/mL.

Placebo will be vehicle.

Setmelanotide and placebo are clear, colorless to slightly opalescent solutions essentially free of visible particulates, and are suitable for a double-blind study. Setmelanotide and placebo will be administered as SC injection once daily.

All study drug must be kept in a secure, limited-access storage area at a temperature between 2°C to 8°C. Both setmelanotide and placebo are stable at room temperature for a short period that will allow patients to transport study drug home; ice packs and cooler bags will be provided for patients and caretakers who will travel long distances from the clinic. Patients will be encouraged to proceed directly home after clinic visits in which study drug is dispensed to minimize the amount of time the study drug is exposed to elevated temperatures.

A separate pharmacy manual with specific instructions will be provided to the investigative site.

There will be extensive training of patients in drug administration including educational materials. Study specific training materials will be provided to both the investigative staff and study participants and caregivers. Rhythm will provide extra placebo supplies for use during training.

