5.2. Study Drug Dose and Administration

Study patients will receive study drug by SC injection once daily (administered in the morning). The dose titration phase will consist of a dose titration phase of up to 10 weeks. Once the patient's therapeutic dose is determined, the same dose/volume will be administered throughout the remainder of the study.

The goal is for the patient or their caretaker to successfully self-administer the study drug themselves at home. Given the rarity of LEPR patients, arrangements may be made for those who are not able to successfully self-administer the study drug to have assistance by a visiting home health care practitioner.

Patients and/or their caretakers (including home health practitioners) will be responsible for all procedures associated with study drug administration, i.e., drawing up, and self-administering the study drug once daily (including during the practice periods).

To ensure patients or their caregivers can successfully self-administer study drug, a training period in the clinic with placebo (or saline) during screening will occur before entering the open label dose titration phase. This training/practice period can occur as many times as necessary throughout the study to assure proper technique. The training/practice period does not pertain to the home health practitioners.

Patients will be required to fast overnight for all clinic visits. Water will be allowed throughout the fasting period.

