5.4.2. Packaging and Labeling

All study drugs, including placebo for practice, will be supplied by Rhythm.

Packaging and labeling will be prepared to meet all regulatory requirements.

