18 Safety laboratories will include: CBC with platelet count and standard indices, chemistry panel (includes sodium, potassium, chloride, CO₂, albumin, total protein, glucose, BUN, creatinine, uric acid, AST, ALT, GGT, CPK, alkaline phosphatase, total bilirubin, direct bilirubin, LDH, calcium, phosphorus), urinalysis with microscopic analysis if positive findings on dipsticks warrant further examination. Safety laboratories shall also include a coagulation profile (prothrombin time [PT] or international normalized ratio [INR], and partial thromboplastin time [PTT], also referred to as activated partial thromboplastin time [aPTT]. Fasting samples (8 hours minimum) are required at all timepoints where feasible. [REDACTED] and HbA1c will also be included.

19

20 Daily hunger questionnaire scores will be assessed by asking the patient to score their hunger
[REDACTED] Daily hunger questionnaire scores will be recorded daily, prior to the patient's morning meal.

21 [REDACTED]

22 [REDACTED]

23 Body composition may be performed using an appropriate method available at sites (e.g. BIA, DXA, etc.). Refer to Section 6.3.3 regarding appropriate methodology for assessing this patient population.

24 Once all the pre-dose assessments have been performed, the decision to dose titrate per Appendix 11.8 will be made. If the patient's therapeutic dose has been established, the patient will transition into the 10-week Open Label Active Treatment Phase, receive their therapeutic dose, and complete the V3 post-dose assessments as defined in the SOA. If the patient's therapeutic dose has not been established per Appendix 11.8, the patient will be administered study drug, complete the dose titration post-dose assessments as defined in the V2 SOA, and return to the clinic in ~2 weeks for the next sequential Visit 2 (i.e.; V2b, V2c, etc.).

25 Adverse events will be recorded from the time a patient provides informed consent. AEs reported after dosing on Day 1 will be considered treatment-emergent AEs.

26 Any patients with positive anti-drug antibodies will be followed ~every 3 months until titers resolve or return to baseline.

27 Telephone contact by site monthly, or more frequently, if needed.

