7. ADVERSE EVENTS

Monitoring of adverse events will be conducted throughout the study. Adverse events will be recorded in the CRFs from Screening through the Final Study Visit. Adverse events that occur after the start of study drug administration will be considered treatment emergent adverse events (TEAEs). SAEs will be recorded through the Final Study Visit. All adverse events should be monitored until they are resolved or are clearly determined to be due to a patient's stable or chronic condition or intercurrent illness(es).

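### Schedule footnote 25 classes adverse events as treatment-emergent by report time, Section 7 by occurrence, so an event that began in screening but was reported late can be miscounted

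*Protocol*

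**What the plan says.** Two statements in the protocol define a treatment-emergent event.

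- Table 6-1, footnote 25 (Section 6.1): "AEs reported after dosing on Day 1 will be considered treatment-emergent AEs". The sentence before it sets the start of collection: "Adverse events will be recorded from the time a patient provides informed consent".
- Section 7: "Adverse events that occur after the start of study drug administration will be considered treatment emergent adverse events (TEAEs").

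The meaning of study drug bears on the second. Section 5.1 says "All investigational study drugs (setmelanotide and placebo) will be supplied by Rhythm". Section 5.4.2 says "All study drugs, including placebo for practice, will be supplied by Rhythm". Section 5.2 makes patients and caretakers responsible for "drawing up, and self-administering the study drug once daily (including during the practice periods"), and places practice before titration: "a training period in the clinic with placebo (or saline) during screening will occur before entering the open label dose titration phase". Against these, footnote 13 to Table 6-1 has study drug starting on the morning of Day 1.

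Section 8.2 anchors the baseline value for every endpoint to the first dose of active treatment. Neither TEAE definition uses that anchor.

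**The concern.** A treatment-emergent classification is meant to separate what began or worsened on the drug from what was already present. A rule based on report time does not do this: it classifies by when the patient mentioned the event. A rule based on occurrence does, provided its starting point is clear. The protocol states one of each, and they give different answers for the same event.

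Safety and tolerability is the first secondary objective in Section 2.1.2, and Section 2.2 assesses it by the frequency and severity of AEs. Outside the withdrawal phase there is no concurrent control to show how often such events arise without the drug, and with so few patients a single event is visible in any percentage.

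**Working it through.** The protocol gives no figure to reproduce. The check sets the two rules side by side and applies them to example events.

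**Inputs**
- Collection of AEs starts at consent (footnote 25).
- Screening lasts two to four weeks (Sections 5.5 and 6.1).
- The first setmelanotide dose is given at the start of titration week 1 (Section 5.2.1).
- Practice injections, with placebo or saline, take place in screening (Section 5.2).
- Planned enrolment is about 10 (Synopsis).

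**Classification: is the event treatment-emergent?**

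| Event | Footnote 25 | Section 7, clock from Day 1 | Section 7, clock from practice placebo | Onset on or after first setmelanotide dose |
|---|---|---|---|---|
| A. Begins in screening before any practice injection, first reported after the Day 1 dose | Yes | No | No | No |
| B. Begins in screening after practice placebo, reported before the Day 1 dose | No | No | Yes | No |
| C. Begins in screening after practice placebo, first reported after the Day 1 dose | Yes | No | Yes | No |
| D. Begins after the Day 1 dose | Yes | Yes | Yes | Yes |

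Events A and C show the conflict. Footnote 25 counts them although they began before setmelanotide; Section 7 with a Day 1 start does not. An event cannot be reported before it begins, so footnote 25 captures every new event with onset after the Day 1 dose (row D). For new events its error therefore runs in one direction only, towards over-counting.

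Events B and C show the ambiguity in Section 7. They are treatment-emergent under it only if a practice injection starts the clock.

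**Can events A and C arise?** Yes. Collection is open throughout screening. In Table 6-1A most assessments at visit V2a carry the superscript for completion before dosing, but the AE assessment does not, so the schedule does not require AEs to be elicited before the first dose.

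**Scale.** One patient wrongly counted changes a patient-level incidence by 1/N. With N = 10, 1/10 = 10 percentage points. The number of patients affected is not given and cannot be derived from the protocol.

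**The case against.** The strongest reply is that this is one loose word in a footnote, and that several provisions limit the harm.

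- Section 6.4.2 requires a recent medical history on Day 1 before the first dose, covering changes since screening, and AEs are also assessed at screening. This narrows the gap but does not close it, and nothing says that the history settles TEAE status.
- Section 8.2 names no treatment-emergent table. It summarises AEs generally and lists them by patient with onset dates, so a misclassified event could be traced. This stands, and it limits the consequence.
- Analysis conventions are deferred to a SAP that is not shown. That would answer a complaint about missing detail. Here the protocol states the definition twice, with different results, and a SAP could agree with at most one of them.

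A reader might infer more: that Section 7 also places pre-setmelanotide events among the TEAEs, because study drug there includes practice placebo. The document does not support this as a firm conclusion. Footnote 13 starts study drug on Day 1, Table 6-1A lists placebo practice on a separate row from study treatment administration, and practice may use saline. The sentences that stretch the term concern who supplies the product and who injects it; neither sets a start date. A reader might also infer that misclassified events are bound to occur, or that a treatment-emergent table is the main safety output. The protocol establishes neither.

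**Conclusion.** The conflict between the two definitions is in the current text. Footnote 25, followed literally, gives a wrong result for an event with onset in screening that is first reported after the Day 1 dose. Section 7 contains an ambiguity about when the clock starts, not a certain error.

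The effect is minor: a possible small over-count of TEAEs, confined to the safety summaries. At about 10 patients each misclassified patient is worth about 10 percentage points on an incidence, but the protocol gives no basis for expecting more than an occasional case. The primary endpoint and AE collection are unaffected. The conclusion assumes that footnote 25 would be applied as written and that the safety summaries use the TEAE classification.

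**What to change.** In footnote 25, replace the report-based rule with one based on onset: an event is treatment-emergent if it begins, or a pre-existing condition worsens, on or after the first dose of setmelanotide, whatever the date of report. Put the same definition in Section 7, and have the SAP follow it. This matches the active-treatment anchor that Section 8.2 already uses for baseline, and it stops a practice placebo injection from starting the clock in screening. Events between consent and that dose, including any after practice injections, would then be listed as pre-treatment.

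The cost is one sentence in two places. Onset dates are already planned for the patient listing, so no visit, form or analysis of efficacy changes.
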